6.2.2.3 Rescue Medications and Supportive Care Guidelines for Pembrolizumab

Subjects should receive appropriate supportive care measures as deemed necessary by the treating investigator including, but not limited to, the items outlined in [Table 3](#).

Suggested supportive care measures for the management of adverse events with potential immunologic etiology are outlined in [Table 3](#). Where appropriate, these guidelines include the use of oral or intravenous treatment with corticosteroids as well as additional anti-inflammatory agents if symptoms do not improve with administration of corticosteroids. Note that several courses of steroid tapering may be necessary as symptoms may worsen when the steroid dose is decreased. For each disorder, attempts should be made to rule out other causes such as metastatic disease or bacterial or viral infection, which might require additional supportive care. The treatment guidelines are intended to be applied when the investigator determines the events to be related to pembrolizumab.

Note: If after the evaluation the event is determined not to be related, the investigator does not need to follow the treatment guidance (as outlined in [Table 3](#)). Refer to [Section 6.2.1.2](#) for dose modification.

It may be necessary to perform additional procedures such as bronchoscopy, endoscopy, or skin photography as part of evaluation of the event.

6.2.2.3.1 Dose Modification and Toxicity Management of Infusion Reactions Related to Pembrolizumab

Pembrolizumab may cause severe or life threatening infusion reaction including severe hypersensitivity or anaphylaxis. Signs and symptoms usually develop during or shortly after drug infusion and generally resolve completely within 24 hours of completion of infusion. Dose modification and toxicity management guidelines on pembrolizumab-associated infusion reaction are provided in [Table 4](#).

Approved

Table 4. Pembrolizumab Infusion Reaction Dose Modification and Treatment Guidelines

NCI CTCAE Grade	Treatment	Premedication at Subsequent Dosing
Grade 1 Mild reaction; infusion interruption not indicated; intervention not indicated	Increase monitoring of vital signs as medically indicated until the participant is deemed medically stable in the opinion of the investigator.	None
Grade 2 Requires therapy or infusion interruption but responds promptly to symptomatic treatment (eg, antihistamines, non-steroidal anti-inflammatory drugs [NSAIDs], narcotics, intravenous [IV] fluids); prophylactic medications indicated for ≤ 24 hrs.	Stop Infusion. Additional appropriate medical therapy may include but is not limited to: IV fluids Antihistamines NSAIDs Acetaminophen Narcotics Increase monitoring of vital signs as medically indicated until the participant is deemed medically stable in the opinion of the investigator. If symptoms resolve within 1 hour of stopping drug infusion, the infusion may be restarted at 50% of the original infusion rate (eg, from 100 mL/hr to 50 mL/hr.). Otherwise dosing will be held until symptoms resolve and the participant should be premedicated for the next scheduled dose. Participants who develop Grade 2 toxicity despite adequate premedication should be permanently discontinued from further study drug treatment.	Participant may be premedicated 1.5 h (± 30 minutes) prior to infusion of _____ with: Diphenhydramine 50 mg po (or equivalent dose of antihistamine). Acetaminophen 500-1000 mg po (or equivalent dose of analgesic).

Approved

Table 4. Pembrolizumab Infusion Reaction Dose Modification and Treatment Guidelines

NCI CTCAE Grade	Treatment	Premedication at Subsequent Dosing

Grades 3 or 4
 
Grade 3: Prolonged (ie, not rapidly responsive to symptomatic medication and/or brief interruption of infusion); recurrence of symptoms following initial improvement; hospitalization indicated for other clinical sequelae (eg, renal impairment, pulmonary infiltrates)
 
Grade 4: Life-threatening; pressor or ventilator support indicated
	
Stop Infusion.
 
Additional appropriate medical therapy may include but is not limited to:
 
Epinephrine**
 
IV fluids
 
Antihistamines
 
NSAIDs
 
Acetaminophen
 
Narcotics
 
Oxygen
 
Pressors
 
Corticosteroids
 
Increase monitoring of vital signs as medically indicated until the participant is deemed medically stable in the opinion of the investigator.
 
Hospitalization may be indicated.
 
**In cases of anaphylaxis, epinephrine should be used immediately.
 
Participant is permanently discontinued from further study drug treatment.
	
No subsequent dosing

Approved

** Appropriate resuscitation equipment should be available at the bedside and a physician readily available during the period of drug administration. For further information, please refer to the Common Terminology Criteria for Adverse Events v4.0 (CTCAE) at <http://ctep.cancer.gov>

6.2.2.4 Diet and Other Considerations While Taking Pembrolizumab

6.2.2.4.1 Diet During Treatment With Pembrolizumab

Subjects should maintain a normal diet unless modifications are required to manage adverse events such as diarrhea, nausea, or vomiting.

6.2.2.4.2 Contraception Requirement for Pembrolizumab

Pembrolizumab may have adverse effects on a fetus in utero. Furthermore, it is not known if pembrolizumab has transient adverse effects on the composition of sperm.

Subjects should be informed that taking pembrolizumab may involve unknown risks to the fetus (unborn baby) if pregnancy were to occur during the study. In order to participate in the study, men and women of reproductive potential must adhere to the contraception requirements (See [Section 4.1.2](#), exclusion criteria 220 and 221) from the day of pembrolizumab initiation (or 14 days prior to the initiation of pembrolizumab for oral contraception) throughout the study period up to 120 days after the last dose of pembrolizumab. If there is any question that a subject of reproductive potential will not reliably comply with the requirements for contraception, that subject should not be enrolled into the study.

6.2.2.4.3 Use of Pembrolizumab in Pregnancy

If a subject inadvertently becomes pregnant while on treatment with pembrolizumab, the subject will immediately be removed from the study. The outcome of the pregnancy will be reported to Amgen and followed as described in [Section 9.3](#) (Pregnancy and Lactation Reporting).

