All subjects who permanently discontinue study drug for any reason other than withdrawal of full consent will be contacted by clinic visit or telephone to assess survival, initiation of additional melanoma therapy, and whether any injected investigational product-related AE has occurred. Contact for all subjects will be attempted every 12 weeks (\pm 28 days) following the safety follow-up visit until death, subject withdraws full consent, or up to 60 months after the end of randomization of phase 3. The sponsor may request survival status to be assessed at additional time points during the course of the study.

Clinical, radiographic, photographic tumor assessments, and tumor response assessment per modified irRC (phase 1b) or modified irRC-RECIST (phase 3) and completion of PRO questionnaires will be performed every 12 weeks (+1 week) until a documented confirmed progressive disease (PD) per modified irRC (phase 1b) or iPD per modified irRC-RECIST (phase 3), start of new anticancer treatment, death, or end of study, whichever occurs first. For subjects with progressive disease (see footnote cc of [Table 6](#)), QLQ-C30 will no longer be collected, and EuroQoL-5D-3 Level (EQ-5D-3L) will be collected through the long-term follow-up.

Blood for anti-pembrolizumab antibody and blood for PK of pembrolizumab will be collected at 3 and 6 months after study discontinuation or up until the subject starts new anticancer therapy, whichever occurs first. Antibody and PK sample collection may be discontinued if ongoing antibody and PK results from this study continue to be consistent with existing data from other pembrolizumab melanoma clinical trials.

All subjects treated with talimogene laherparepvec (all subjects in phase 1b and those who received talimogene laherparepvec in phase 3) and who permanently discontinue study will be eligible to continue follow-up for survival under an ongoing separate registry protocol that is in place for the long-term follow-up of subjects treated with talimogene laherparepvec in clinical trials. The registry protocol, including for phase 1b subjects, will not apply until the end of the study or 5 years after the last subject is enrolled in phase 3, whichever comes first. The registry protocol will also monitor for late and long-term adverse events thought to be potentially related to talimogene laherparepvec.

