3.5 Estimated Study Duration

3.5.1 Study Duration for Subjects

The duration for the study from the initiation of phase 1b is approximately 8 years (96 months). The duration of screening for each subject will be approximately 28 days. The subject accrual period for phase 1b is planned for approximately 6 months from the initiation of phase 1b. The subject accrual period for phase 3 is planned for approximately 20 months (depending on average per month enrollment rates) from the initiation of phase 3. The duration of treatment will vary for each subject. Subjects enrolled in phase 1b and phase 3 parts of the study will be treated for up to approximately 24 months. Subjects will be followed for safety approximately 30 (+7) days after the last dose of study treatment and for serious adverse event reporting approximately 90 (+7) days after the cessation of all study treatment or 30 (+7) days following cessation of treatment if the subject initiates new anticancer therapy, whichever is earlier. If an end of treatment decision occurs > 30 (+7) days after the last treatment date, then the Safety follow-up should be performed as soon as possible (eg, within a week of the end of treatment decision). Subjects will be followed for survival for approximately 60 months after the last subject is randomized in phase 3.

The end of study for each subject is defined as the date the subject withdraws full consent from the study, completes the safety follow-up visit or the long-term survival follow-up, whichever is later, or death.

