7.2.3 Safety Follow-up Visit

Upon permanent discontinuation from the study treatment for any reason, the following procedures will be performed approximately 30 (+7) days after the last dose of talimogene laherparepvec or the last dose of pembrolizumab, whichever is later. If an end of treatment decision occurs > 30 (+7) days after the last treatment date, then the safety follow-up should be performed as soon as possible (eg, within a week of the end of treatment decision). Applicable safety follow-up procedures should occur even if the subject has initiated new anticancer therapy.

Phase 1b and 3:

- Vital signs (systolic/diastolic blood pressure, heart rate, respiration rate, temperature): Subject must be in a supine position in a rested and calm state for at least 5 minutes before blood pressure assessments are conducted. If the subject is unable to be in the supine position, the subject should be in most recumbent position possible. The position selected for a subject should be the same that is used throughout the study and be documented on the vital sign CRF.

- Physical examination including body weight as per standard of care
- ECOG performance status assessment
- A 12-lead ECG. The ECG must include the following measurements: heart rate, PR, QRS, QT and QTc intervals.
- Local laboratory Assessments: Tests can be performed within 3 days of the planned visit.
 - hematology panel: hemoglobin, hematocrit, WBC count with 5-part differential (3-part differential if 5-part unable to be performed), RBC count, platelets
 - chemistry panel: sodium, potassium, chloride, calcium, magnesium, phosphorus, uric acid, total protein, albumin, BUN (phase 1b only), BUN/urea (phase 3), creatinine, total bilirubin, alkaline phosphatase, AST, ALT, glucose
 - LDH test (phase 3 only)
 - thyroid function tests: T3 (or FT3 per local standard), FT4, TSH
 - serum or urine pregnancy test for female subjects of childbearing potential
 - urinalysis (blood, glucose, protein, specific gravity) and reflexive microscopic exam only for any abnormal urinalysis results
- Central laboratory assessments:
 - Swab of cold sore, vesicles and other lesions suspected to be herpetic in origin (if any) for qPCR testing of talimogene laherparepvec DNA:

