7.2.4 Long-term Follow-up

All subjects who permanently discontinue study drug for any reason other than withdraw of full consent will be contacted by clinic visit or telephone to assess survival, initiation of additional melanoma therapy, and whether any injected investigational product-related adverse events has occurred.

Contact for all subjects will be attempted every 12 weeks (\pm 28 days) following the safety follow-up visit until death, subject withdraws full consent, or up to 60 months after the end of randomization of phase 3. The sponsor may request survival status to be assessed at additional time points during the course of the study.

For subjects discontinuing study treatment without a documented confirmed PD, clinical tumor assessment (phase 1b only), radiographic imaging, photographic imaging, and tumor response assessment as detailed in [Section 7.2.2](#) and PRO (EQ-5D-3L and QLQ-C30) questionnaires will be performed every 12 weeks (+1 week) or more frequently if clinically indicated until documented confirmed PD per modified irRC in phase 1b ([Appendix D](#)) or iPD per modified irRC-RECIST in phase 3 ([Appendix F](#)), start of new anticancer treatment, death, or end of study, whichever occurs first. For subjects with progressive disease, QLQ-C30 will no longer be collected, and EQ-5D-3L will be collected through the long-term follow-up. Subjects who have reached a confirmed CR may increase their interval of radiographic assessments up to 6 months after the first 2 years beyond confirmed CR and up to 12 months after the first 5 years beyond confirmed CR as long as CR is maintained.

[figure not shown]
Approved

Blood for anti-pembrolizumab antibody and blood for PK of pembrolizumab will be collected at 3 and 6 months after study discontinuation or up until the subject starts new anticancer therapy, whichever occurs first. Anti-pembrolizumab antibody and pembrolizumab PK sample collection and analyses in phase 3 may be discontinued if ongoing antibody and PK results from this study continue to be consistent with existing antibody and PK data from other pembrolizumab melanoma clinical trials.

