8. WITHDRAWAL FROM TREATMENT, PROCEDURES, AND STUDY

8.1 Subjects' Decision to Withdraw

Subjects have the right to withdraw from the study at any time and for any reason without prejudice to their future medical care by the physician or at the institution.

Subjects (or a legally acceptable representative) can decline to continue receiving investigational product and/or other protocol-required therapies or procedures at any time during the study but continue participation in the study. If this occurs, the investigator is to discuss with the subject the appropriate processes for discontinuation from investigational product or other protocol-required therapies and must discuss with the subject the options for continuation of the Schedule of Assessments ([Table 5](#) and [Table 6](#)) including different options for follow-up (eg, in person, by phone/email, through family/friends, in correspondence/communication with other treating physicians, the review of medical records) and collection of data, including endpoints and adverse events. Subjects that have discontinued investigational product and/or protocol required therapies or procedures should not be automatically removed from the study. Whenever safe and feasible, it is imperative that subjects remain on study to undergo safety surveillance and/or collection of outcome data. The investigator must document the change to the Schedule of Assessments ([Table 5](#) and [Table 6](#)) and the level of follow-up that is agreed to by the subject (eg, in person, by telephone/mail, through family/friends, in correspondence/communication with other physicians, from review of the medical records).

For subjects who discontinue investigational product without documented PD and have not initiated a new anticancer therapy, every effort should be made to continue monitoring tumor response status by clinical and radiographic tumor assessments, and to complete PRO questionnaires as described in [Table 6](#).

Those subjects who discontinue investigational product should continue into the long-term follow-up. Subjects will be followed for survival and subsequent anticancer therapies every 12 weeks (\pm 28 days) for approximately 60 months after the last subject is enrolled in phase 3. In addition, talimogene laherparepvec- or placebo-related adverse events that occur through the end of the long-term follow-up will be reported.

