For those subjects who are randomized but do not receive any doses of investigational product, every effort should be made to continue monitoring tumor response status by clinical and radiographic tumor assessments as described in [Table 6](#). They should continue into the long-term follow-up and be followed for survival and subsequent

anticancer therapies every 12 weeks (\pm 28 days) for approximately 60 months after the last subject is enrolled in phase 3.

Withdrawal of consent for a study means that the subject does not wish to receive further protocol-required therapies or procedures, and the subject does not wish to or is unable to continue further study participation. Subject data up to withdrawal of consent will be included in the analysis of the study, and where permitted, publicly available data can be included after withdrawal of consent. The investigator is to discuss with the subject appropriate procedures for withdrawal from the study.

8.2 Investigator or Sponsor Decision to Withdraw or Terminate Subjects' Participation Prior to Study Completion

The investigator and/or sponsor can decide to withdraw a subject from investigational products and/or other protocol-required therapies, protocol procedures, or the study as a whole at any time prior to study completion.

Subjects may be eligible for continued treatment with Amgen investigational product and/or other protocol-required therapies by a separate protocol or as provided for by the local country's regulatory mechanism, based on parameters consistent with [Section 12.1](#).

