8.3.2 Reasons for Removal From Study

Reasons for removal of a subject from the study are:

- decision by sponsor
- full withdrawal of consent from study
- death
- lost to follow-up

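### Protocol 6.2.2.4.3 takes a subject who becomes pregnant on pembrolizumab out of the study, while 7.2.4 and the synopsis keep everyone who stops study drug in follow-up unless consent is fully withdrawn

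*Protocol*

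**What the plan says.** The rule in question is Protocol 6.2.2.4.3: "If a subject inadvertently becomes pregnant while on treatment with pembrolizumab, the subject will immediately be removed from the study". Its next sentence sends the outcome of the pregnancy to Section 9.3 for reporting and follow-up.

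The follow-up rule is Protocol 7.2.4: "All subjects who permanently discontinue study drug for any reason other than withdraw of full consent will be contacted by clinic visit or telephone". Contact is attempted every 12 weeks until death, full withdrawal of consent, or 60 months after phase 3 randomization closes. It covers survival, new melanoma therapy and adverse events related to the injected product. The synopsis, under Long-Term Follow-up Procedures, repeats it: "All subjects who permanently discontinue study drug for any reason other than withdrawal of full consent will be contacted by clinic visit or telephone".

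Other sections bear on how the two should be read:

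- Section 7.2.3 sets the safety visit: "Upon permanent discontinuation from the study treatment for any reason, the following procedures will be performed".
- Section 8.1 states: "Those subjects who discontinue investigational product should continue into the long-term follow-up". It also says that stopping product should not lead to automatic removal from the study.
- Section 8.2 is permissive: "The investigator and/or sponsor can decide to withdraw a subject from investigational products". It extends that option to procedures and to the study as a whole.
- Section 8.3.1 names pregnancy among the reasons for leaving treatment or procedural assessments.
- Section 6.2.1.2 makes pregnancy a reason to stop talimogene laherparepvec or placebo.
- Section 8.3.2 opens with "Reasons for removal of a subject from the study are" and gives four entries: sponsor decision, full withdrawal of consent, death and loss to follow-up.
- Section 3.5.1 begins "The end of study for each subject is defined as the date the subject withdraws full consent from the study" and adds completion of safety or long-term follow-up, and death.

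**The concern.** The two instructions give different answers for the same woman. One site could close her participation on the day pregnancy is found. Another, working from 7.2.4, would keep contacting her every 12 weeks.

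Under the literal reading, a randomized subject stays in the full analysis set (Protocol 10.1.2; SAP 7.2), but planned survival contact and long-term collection of injected-product-related adverse events stop. SAP Section 6 then censors her OS at the last date she is known to be alive. SAP 10.5.4.2 treats censoring more than 140 days before the data cutoff as potentially informative and examines it in a Fine-Gray sensitivity analysis, but that analysis cannot restore follow-up that was never collected.

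There is also a safety argument. The product is derived from HSV-1, and exclusion criterion 227 counts pregnant women among those at higher risk of HSV-1 complications. This is a poor subject in whom to end planned safety collection. The registry described in 7.2.4 does not fill the gap, because it does not apply until the end of the study or five years after the last phase 3 enrollment.

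**Working it through.** No formula decides this point. The check is a comparison of text, followed by a simple statement of size.

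**1. Do the rules cover the same subject?** Yes. A subject who becomes pregnant on pembrolizumab stops study drug for good: 8.3.1 lists pregnancy as a reason to end treatment, and 6.2.1.2 stops the injected product. She therefore falls within 7.2.4, which makes no exception for pregnancy.

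**2. Do they require different things?**

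| | Section 6.2.2.4.3 | Section 7.2.4 and synopsis |
|---|---|---|
| Trigger | Pregnancy on pembrolizumab | Stopping study drug |
| Consequence | Immediate removal from the study | Contact every 12 weeks |
| Named exception | None | Full withdrawal of consent |

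The consequences are incompatible. Section 8.3 has separate headings for removal from treatment and removal from study, so a site has reason to take the word study at face value.

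**3. Does another section reconcile them?** Not clearly. Sponsor decision in 8.3.2 could cover such a removal, but 8.2 words that power as an option, while 6.2.2.4.3 is automatic and does not refer to it.

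**4. Which reading do the other sections favour?** Treatment only. Section 8.1 sends those who stop product into long-term follow-up and warns against automatic removal. Section 8.3.1 places pregnancy under removal from treatment or procedural assessments. Section 6.2.1.2 attaches to pregnancy only the stopping of the injected product. Sections 8.3.2 and 3.5.1 do not mention pregnancy, which fits this reading but is supporting evidence only.

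**5. What would remain under the literal reading?**

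- Section 9.3 still provides for pregnancy reporting, birth outcome and infant health. It does not provide 12-weekly survival contact or long-term collection of injected-product-related events.
- Section 9.2.1.2 still has the investigator report serious adverse events that come to notice after the reporting period.
- Section 12.4 allows survival status to be sought in public records where permitted.

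The loss is therefore partial.

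**6. Size.** The documents give no expected number of pregnancies. The share for one subject is:

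- planned phase 3 size (Protocol 10.2.2): 1/660 = 0.15%;
- number implied by SAP Table 5, where maximum information for iCRR is 692 and SAP 8.1.4 defines that maximum as all randomized subjects: 1/692 = 0.14%.

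The PFS and OS primary analyses are triggered by 407 and 346 events, so one or a few subjects censored early would have a negligible effect on either test.

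**The case against.** The strongest reply is that this is a drafting slip that no sensible site would follow. The sentence stands in the treatment section, among the considerations for a subject taking pembrolizumab, and Section 8 governs withdrawal. Read together, the sections favour removal from treatment. Contraception and a negative pregnancy test within 72 hours before enrollment make the event uncommon, and with treatment limited to 24 months an amendment would reach only subjects still on treatment.

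Most of that stands, and it is why the point is minor. It does not make the sentence correct. If the specific rule is meant to prevail, 7.2.4 lacks an exception. If it is not, 6.2.2.4.3 names the wrong consequence. Either way the text needs correcting.

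The objection also limits what can be built on the sentence. A reader might infer three stronger conclusions that the documents do not support:

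- **That 8.3.2 and 3.5.1 contradict it independently.** Section 3.5.1 also omits sponsor decision and loss to follow-up, both of which 8.3.2 accepts, so its silence on pregnancy proves little. Section 8.3.2 includes sponsor decision, which leaves some room. The clear conflict is with 7.2.4 and the synopsis.
- **That the safety visit is plainly lost.** Section 7.2.3 is triggered by the end of treatment, whatever the reason. A pregnant subject meets that trigger, and 6.2.2.4.3 does not expressly cancel the visit.
- **That a minimum gap before the OS cutoff can be calculated.** From Table 9 and the 24-month treatment limit, the time from stopping treatment to the estimated OS primary analysis is at least 75 - 26 - 24 = 25 months, or 25 x 30.4375 = 761 days. That is not a floor on time without a known vital status. Contact under 9.3 can supply a later date alive, and the SAP's list of sources for that date is open. If delivery is assumed about 270 days later, the gap is 761 - 270 = 491 days. This still exceeds 140 days, but it is an illustration and not a bound.

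**Conclusion.** The concern holds as a minor internal inconsistency. Protocol 6.2.2.4.3 is wrong as written, because it automatically ends participation for a subject whom 7.2.4 and the synopsis keep in follow-up. The most likely intention is removal from study treatment, but a reader has to infer that from other sections.

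The number of subjects affected is unknown. Each would be about 0.14% to 0.15% of those randomized, and the effect on the PFS and OS tests is negligible, assuming that pregnancies on treatment number at most a few. No specific PFS consequence is claimed, because 8.3.1 itself lets procedural assessments stop on pregnancy. A reader might also infer that the pregnancy outcome goes unrecorded. It does not, because 6.2.2.4.3 and 9.3 require it to be reported and followed. What is at stake is planned survival contact and long-term safety follow-up for an individual subject, and consistent practice across sites.

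**What to change.** In the next amendment, change 6.2.2.4.3 so that, in place of removal from the study, the subject is *permanently discontinued from study treatment; safety and long-term follow-up continue per Sections 7.2.3, 7.2.4 and 9.3 (tumor imaging only where safe and feasible in pregnancy) unless consent is fully withdrawn*.

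The cost is one phrase. It does not justify a stand-alone amendment: Section 12.1 requires investigator agreement and IRB/IEC approval for any amendment, and Section 3.2 plans for approximately 175 sites. It adds no visits beyond the safety and long-term follow-up already planned for subjects who stop treatment, and it needs no change to the SAP.
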